Identifying active ingredients of language interventions for children who are DHH would build our theoretical understanding about what facilitates and impedes their language development. Once identified, active ingredients can be enhanced (e.g., modify intensity) through empirical investigations that consider individual differences. For children who are DHH, **retrieval practice** (testing effect) presents as a potential active ingredient for language intervention. Retrieving previously presented information (e.g., answering questions or free recall) is **hypothesized to enhance encoding and retention** because it entails the desirable level of effort (desirable difficulties hypothesis; Bjork & Bjork, 2011; Bjork, 1994), builds semantic elaborations and associations between words (elaborative retrieval account; Carpenter, 2009; Carpenter & Yeung, 2017), and/or updates representations to reflect multiple contexts (episodic context account; Karpicke et al., 2014). Replicated findings in children and adults with typical development (Fritz et al., 2007; Goossens et al., 2014; Jones et al., 2016; Karpicke et al., 2014, 2016; Lipowski et al., 2014; Marsh et al., 2012) and emerging results for individuals with disabilities (Coyne et al., 2015; Haebig et al., 2019; Knouse et al., 2016; Leonard, Deevy, et al., 2019; Leonard, Karpicke, et al., 2019; McGregor et al., 2017) have showed positive effects of retrieval practice for academically relevant tasks (e.g., word learning, textbook content, and recalling word lists or pairs) over short retention periods (e.g., one session or one week). For children who are DHH, the few experimental studies on language intervention have often used retrieval practice to some degree, though typically without isolating retrieval practice's effect and under another name (e.g., choral responses, cloze procedures, and receptive and expressive practice; Bobzien et al., 2015; Lund & Douglas, 2016; McDaniel et al., 2019; McDaniel et al., 2018; Reimer, 2019).

Antia, S. D., Lederberg, A. R., Easterbrooks, S., Schick, B., Branum-Martin, L., Connor, C. M., & Webb, M.-Y. (2020). Language and reading progress of young deaf and hard-of-hearing children. *Journal of Deaf Studies and Deaf Education* [advanced online release].

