2.0 Rationale and Specific Aims

This study is designed to test the effectiveness and efficiency of retrieval practice for word learning for children who are DHH.

Aim 1: Evaluate the effectiveness and efficiency of retrieval practice with and without feedback for the acquisition and retention for learning novel words. Both conditions are hypothesized to be effective with the feedback condition (i.e., explicit responses about accuracy given to child during teaching sessions) being more efficient than no feedback. Feedback is predicted to improve efficiency because it focuses the child's attention on unmastered material, prevents the illusion of success, and reduces repeated error.

Aim 2: Evaluate the effectiveness and efficiency of retrieval practice with spaced versus massed trials for the acquisition and retention for learning novel words. Both conditions are hypothesized to be effective with spaced trials (i.e., words are interspersed with one another) yielding more efficient learning than massed trials because spaced trials require more effort with fewer cues provided.

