(Ledford & Gast, 2018). Training includes reading the coding manual, a didactic presentation, and group coding of non-participants with discrepancy discussions prior to independent coding. Discrepancy discussions occur regularly. If IOA falls below .85 for two sessions, coders must re-train to the initial training criteria.

Baseline Phase

Baseline sessions will occur three times per week and continue until the participant demonstrates a stable pattern of response, with a minimum of three sessions (Ledford & Gast, 2018). Participants complete a listening check then the dependent variable probe to test learning of the 12 target words.

Comparison Phase

Comparison phase sessions occur three times per week after the baseline phase is complete. They begin with a listening check, then the dependent variable probe, and then the two retrieval practice intervention conditions (i.e., feedback-massed, no feedback-massed, feedback-spaced, and no feedback-spaced) for the participant's specific, randomly assigned contrast. In each session, the second condition occurs immediately after the first. Participants are taught the meaning of novel nouns (Lund & Douglas, 2016; Reimer, 2019; Storkel et al., 2019). The independent variable that differentiates the conditions is either the presence of feedback or spaced versus massed trials. All other potentially influential variables are held constant. Table 1 provides a summary of the key teaching procedures for the massed trials conditions (with and without feedback). For the massed trials conditions, all exposures for one word are provided before presenting the next word in an order determined via a random number generator. The spaced trials conditions proceed in the same manner with the exception that the exposures for the four target words are interspersed with one another (e.g., an exposure for word 1, then one for word 3, then one for word 2, etc.). The interspersing of trials across words is especially apparent through the color coding of the steps by word in the Teaching Sessions section of the procedural manual.

Table 1

Summary of Teaching Procedures for Massed Trials Conditions

1. Examiner shows novel object, labels it, and states its location (e.g., "This is a X. The X is from the park.")
2. Examiner and participant color pictures of each novel object to provide shared context
3. Examiner says the label for the novel object ten more times and its location three more times

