Contrasts to Determine Effect of Spacing (RQs 7-12)	Contrast D: Spaced vs. massed trials (with feedback)	Contrast C: Spaced vs. massed trials (no feedback)	

Table 2. *Comparisons of Relevant Conditions for the Effect of Feedback*

Research question		Contrast	Condition 1	Condition 2	Phase	Feedback RQs
Effectiveness or efficiency	Acquisition or retention					
Effectiveness	Acquisition	A	Feedback w/massed trials	No-teaching control	Comparison	1
		B	Feedback w/spaced trials	No-teaching control	Comparison	1
		A	No feedback w/massed trials	No-teaching control	Comparison	2
		B	No feedback w/spaced trials	No-teaching control	Comparison	2
Effectiveness	Retention	A	Feedback w/massed trials	No-teaching control	Maintenance	3
		B	Feedback w/spaced trials	No-teaching control	Maintenance	3
		A	No feedback w/massed trials	No-teaching control	Maintenance	4
		B	No feedback w/spaced trials	No-teaching control	Maintenance	4
Efficiency	Acquisition	A	Feedback w/massed trials	No feedback w/massed trials	Comparison	5
		B	Feedback w/spaced trials	No feedback w/spaced trials	Comparison	5
Efficiency	Retention	A	Feedback w/massed trials	No feedback w/massed trials	Maintenance	6
		B	Feedback w/spaced trials	No feedback w/spaced trials	Maintenance	6

Effectiveness. For research questions related to effectiveness, we determine whether there is an increase in accuracy for the active retrieval practice condition without an

accompanying increase, or with a smaller increase, for the no-teaching control condition. Given that the target words are novel words, participants are not expected to show increased accuracy for the dependent variables for the control condition.

For effectiveness of retrieval practice with feedback for *acquisition* (RQ1), we determine whether there is a separation of the data paths (as indicated by visual analysis and statistical analyses) for (a) the retrieval practice with feedback with massed trials condition and the no-teaching control condition and (b) the retrieval practice with feedback with spaced trials condition and the no-teaching control condition in the comparison phase. This separation of the data paths with the retrieval practice condition above the no-teaching condition in the comparison phase would provide evidence of the effectiveness of retrieval practice with feedback.

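### Eight of the 12 research questions credit retrieval practice with a taught-versus-untaught difference, but no planned comparison separates retrieval from the exposure taught with it

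*Combined protocol and SAP*

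**What the plan says.** Section 1.0 says retrieval practice "presents as a potential active ingredient for language intervention" and describes it as the act of retrieving information already presented. It says that the few earlier experimental studies in children who are DHH often used retrieval practice, "though typically without isolating retrieval practice's effect and under another name". Section 2.0 then gives the purpose: "This study is designed to test the effectiveness and efficiency of retrieval practice for word learning for children who are DHH".

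Each child receives two active conditions and a no-teaching control (section 4.0). Table 1 in section 5.0 lists what an active condition contains. In step 1, "Examiner shows novel object, labels it, and states its location". Step 2 is shared colouring. In step 3, "Examiner says the label for the novel object ten more times and its location three more times". Step 4 has four label prompts and two location prompts, with further examiner labels following. Step 6 closes the set with one more round of prompts. Table 1 describes the massed conditions. The text says the spaced conditions run the same way except that the words are interspersed.

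On how the active conditions differ, the Comparison Phase text says: "The independent variable that differentiates the conditions is either the presence of feedback or spaced versus massed trials". It adds: "All other potentially influential variables are held constant".

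Under Visual Analysis in section 8.0, RQs 1-4 and 7-10 are judged by taught words against no-teaching words, and RQs 5, 6, 11 and 12 by one active condition against the other. The RQ1 rule is that separation with "the retrieval practice condition above the no-teaching condition in the comparison phase would provide evidence of the effectiveness of retrieval practice with feedback". The other seven effectiveness rules repeat this with the condition name changed (without feedback, spaced trials, massed trials) and, for four of the eight, with retention in the maintenance phase.

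**The concern.** The effectiveness comparison changes two things together: whether the child is asked to retrieve the word, and whether the child is taught the word at all. A gap between the data paths is what one would see if retrieval works. It is also what one would see if hearing a label many times beside its object is enough and the prompts add nothing. The rules name only the first explanation.

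The protocol's case for the study is that retrieval may be an active ingredient and that earlier work did not isolate it. If the eight rules are applied as written, the trial could report that retrieval practice is effective for these children on evidence with the same limitation. A practitioner could then favour retrieval prompts over plain repeated labelling, a choice these data would not inform.

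**Working it through.** The plan states no figure on this point, so there is none to reproduce. The check is a count of planned comparisons, a tally of what taught and control words receive, and a test of whether any combination of comparisons isolates retrieval.

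**1. Comparisons by type (Tables 2 and 3, section 8.0)**

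| | Active vs no-teaching | Active vs active | Exposure without retrieval as comparator |
|---|---|---|---|
| Table 2 (feedback) | RQs 1-4, two contrasts each: 4 × 2 = 8 | RQs 5-6: 2 × 2 = 4 | 0 |
| Table 3 (spacing) | RQs 7-10: 4 × 2 = 8 | RQs 11-12: 2 × 2 = 4 | 0 |
| Total | 16 | 8 | 0 of 24 |

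Effectiveness questions: 4 + 4 = 8 of 12.

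**2. What each word receives per teaching session (Table 1, section 5.0)**

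- Examiner labels in steps 1 and 3, which contain no retrieval prompt: at least 1 + 10 = 11, or 2 + 10 = 12 if the step 1 example is counted literally.
- Step 4, one label after each of four label prompts: 11 + 4 = 15, or 12 + 4 = 16. If the label is also said after the two location prompts, which is an assumption, the totals are 17 and 18.
- Location statements in steps 1 and 3: 1 + 3 = 4.
- Label prompts: 4 in step 4 + 1 in step 6 = 5.
- Control words: no teaching labels and no teaching-session prompts. They are probed along with the other words.

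The conclusion does not depend on which label total is right.

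**3. What the comparisons can identify**

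Let E be the gain from exposure (labels, locations, colouring), R the gain from retrieval prompts, and J any joint effect of the two. Take the control words as the reference.

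- Active minus control = E + R + J. A positive value is compatible with R = 0 and J = 0, provided E > 0.
- Active minus active = the effect of feedback or of spacing, in the presence of E and R on both sides. The common parts cancel.

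All four active conditions contain both exposure and retrieval prompts. Any weighted combination of the 24 comparisons therefore contains exposure and retrieval together or neither, and R cannot be recovered.

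**4. Whether another feature closes the gap**

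- *Equal exposures in Table 1, step 4.* The added statement in the no-feedback condition matches it to the feedback condition. This protects the feedback contrast and does nothing for active versus control.
- *Probing of control words.* These words were never taught, so probing them is not retrieval of earlier-presented material, nor does it match the exposure of taught words.
- *Reporting of additional exposures (Procedural Fidelity).* This documents departures from the script and supplies no comparator.

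**The case against.** The strongest reply is that the rules use the names of whole interventions. Section 5.0 refers to the active arms as retrieval practice intervention conditions, and Table 1 spells out their contents. Every effectiveness rule names its no-teaching comparator, and Visual Analysis introduces the eight questions as being about the active interventions. On that reading, retrieval practice with feedback already means the package. The aims also place their directional hypotheses on efficiency, so taught-versus-untaught serves mainly to show that learning occurred. The remark about earlier studies not isolating retrieval promises nothing about this one. And the eight rules are one naming convention repeated, not eight separate errors.

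Part of this stands. The package reading is available, the no-teaching set is a sound check on maturation and repeated testing, and the eight rules share a single cause. It is also fair that control words get some prompts at probes, and probably some label exposure in the receptive task if the examiner says the word. What matters is therefore the difference in exposure, not its mere presence on one side. That difference remains large.

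The reply does not settle the matter, because the documents also use the term narrowly. Section 1.0 describes the act of retrieving, Table 1 attaches the purpose of retrieval practice to the step 4 prompts alone, and Visual Analysis identifies the independent variable as a particular component of retrieval practice. The section 2.0 purpose sentence carries no qualifier. With both senses in use, the rules permit a conclusion about the ingredient that the design cannot support.

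**Conclusion.** The concern holds. As written, the rules for RQs 1-4 and 7-10 would credit retrieval practice with a gain that the design cannot separate from exposure. This touches 8 of 12 research questions and 16 of 24 planned comparisons, and none of the remaining 8 comparisons supplies the missing contrast. Separation would support the teaching package over no teaching.

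The conclusion rests on Table 1 being delivered as described, and on the spaced conditions having the same content as the massed ones, as section 5.0 states. It does not rest on any assumed size for the exposure effect. The documents give no basis for one, so it is possible, not established, that exposure alone would produce the separation. RQs 5, 6, 11 and 12 are unaffected by this point. It should be corrected before results are interpreted.

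**What to change.** Reword the eight effectiveness rules in section 8.0 so that they match the Visual Analysis description of those questions. For RQ1, for example: *evidence that a teaching package including retrieval practice with feedback is effective compared with no teaching*. Use the same form for the without-feedback, spaced, massed and retention rules, and make the same change to the effectiveness part of the purpose and aims in section 2.0.

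Add once to section 8.0: *No condition provides matched exposure without retrieval prompts, so the design does not estimate the effect of retrieval itself; component-level conclusions are limited to feedback (RQs 5-6) and spacing (RQs 11-12).*

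The cost is a narrower stated claim. Procedures, data collection and analysis do not change. A matched-exposure condition without retrieval prompts would be needed to keep the claim about retrieval itself, but that is a change of design and is not required for this correction.

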4. Examiner asks the participant to label the novel object four times and the location twice for retrieval practice

Feedback condition: Examiner provides direct feedback on accuracy and labels the target word (e.g., "Yes, that is a X!" or "Oops, that is a X!")

No-feedback condition: Examiner says statement without target word and then one with it to provide equal exposures to the feedback conditions (e.g., This looks neat. Here's the X!)

5. After the first word, examiner completes same procedure with the three remaining target words in the set
6. Examiner concludes set by asking participant to label and identify the picture for each word and state its location

Feedback condition: Examiner provides direct feedback without naming the target word

No-feedback condition: Examiner does not provide feedback and proceeds to next item

After a participant reaches the criterion of 75% accuracy for expressive labeling for three consecutive sessions for the four target words for one condition, instruction in the remainder of the comparison phase is provided only in the unmastered condition. The comparison phase ends when the unmastered condition reaches criterion. If the participant does not reach mastery after two times the number of sessions to criterion in the mastered condition, the maintenance phase begins then.

Maintenance Phase

Maintenance data are collected weekly via baseline procedures. Maintenance data are first collected a week after the participant achieves mastery for at least one condition. The same dependent variable probe used for the baseline and comparison phases is used to collect maintenance data. Sessions continue for 4 weeks after the comparison phase to permit sufficient time for a trend to emerge for visual analysis. If a consistent pattern is observed before 4 weeks have elapsed, the maintenance phase will end at that time. For example, the maintenance phase ends if a participant exhibits 0% accuracy for all conditions for two consecutive sessions.

Procedural Fidelity

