For effectiveness of retrieval practice without feedback for *acquisition* (RQ2), we determine whether there is a separation of the data paths for (a) the retrieval practice without feedback with massed trials condition and the no-teaching control condition and (b) the retrieval practice without feedback with spaced trials condition and the no-teaching control condition in the comparison phase. This separation of the data paths with the retrieval practice condition above the no-teaching condition in the comparison phase would provide evidence of the effectiveness of retrieval practice without feedback.

For effectiveness of retrieval practice with feedback for *retention* (RQ3), we determine whether there is a separation of the data paths for (a) the retrieval practice with feedback with massed trials condition and the no-teaching control condition and (b) the retrieval practice with feedback with spaced trials condition and the no-teaching control condition in the maintenance phase. This separation of the data paths with the retrieval practice condition above the no-teaching condition in the maintenance phase would provide evidence of the effectiveness of retrieval practice with feedback for retention.

For effectiveness of retrieval practice without feedback for *retention* (RQ4), we determine whether there is a separation of the data paths for (a) the retrieval practice without feedback with massed trials condition and the no-teaching control condition and (b) the retrieval practice without feedback with spaced trials condition and the no-teaching control condition in the maintenance phase. This separation of the data paths with the retrieval practice condition above the no-teaching condition in the maintenance phase would provide evidence of the effectiveness of retrieval practice without feedback for retention.

Efficiency. For research questions related to efficiency, we determine whether there is faster attainment of the mastery criterion for one retrieval practice condition versus another and whether mastery-level performance is better maintained.

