For efficiency of retrieval practice with versus without feedback for *acquisition* (RQ5), we determine whether there is a separation of the data paths for (a) the retrieval practice with feedback with massed trials condition and the retrieval practice without feedback with massed trials condition (Contrast A) and (b) the retrieval practice with feedback with spaced trials condition and the retrieval practice without feedback with spaced trials condition (Contrast B) in the comparison phase. The number of sessions to mastery is

also considered when determining the presence of a functional relation related to efficiency. This separation of the data paths in the comparison phase would provide evidence of greater efficiency for the condition with the path that is displayed higher on the graph.

For efficiency of retrieval practice with versus without feedback for *retention* (RQ6), we determine whether there is a separation of the data paths for (a) the retrieval practice with feedback with massed trials condition and the retrieval practice without feedback with massed trials condition (Contrast A) and (b) the retrieval practice with feedback with spaced trials condition and the retrieval practice without feedback with spaced trials condition (Contrast B) in the maintenance phase. The number of sessions to fall below mastery is also considered when determining the presence of a functional relation related to efficiency. This separation of the data paths in the maintenance phase would provide evidence of greater efficiency for the condition with the path that is displayed higher on the graph.

Spacing. Participants ($n = 8$) in Contrasts C (spaced vs. massed trials without feedback) and D (spaced vs. massed trials with feedback) address the effect of spacing. Table 3 displays how we will compare conditions within Contrasts C and D to evaluate both effectiveness and efficiency research questions. As with the analyses for feedback, we use expressive labeling as the primary dependent variable. Phonological precision, receptive performance, and knowledge of semantic content are secondary variables that will be considered when interpreting the overall results.

Table 3. *Comparisons of Relevant Conditions for the Effect of Spacing*

Research question		Contrast	Condition 1	Condition 2	Phase	Spacing RQs
Effectiveness or efficiency	Acquisition or retention					
Effectiveness	Acquisition	C	No feedback w/spaced trials	No-teaching control	Comparison	7

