For efficiency of retrieval practice with spaced versus massed trials for *retention* (RQ12), we determine whether there is a separation of the data paths for (a) the retrieval practice without feedback with massed trials condition and the retrieval practice without feedback with spaced trials condition (Contrast C) and (b) the retrieval practice with feedback with massed trials condition and the retrieval practice with feedback with spaced trials condition (Contrast D) in the maintenance phase. The number of sessions to fall below mastery is also considered when determining the presence of a functional relation related to efficiency. This separation of the data paths in the maintenance would provide evidence of greater efficiency for the condition with the path that is displayed higher on the graph.

Statistical Analysis

There is no consensus on recommended statistical analyses for single case research designs, particularly for the adapted alternating treatments design, which is underrepresented in research on the use of statistical analyses and effect sizes in single case research. We will calculate Nonoverlap of All Pairs (NAP; Parker & Vannest, 2009), an overlap-based effect size, and analyze differences in conditions analogous to those described for visual analysis. Because overlap is one feature used for determining a functional relation, NAP will provide guidance on the degree of confidence for inferring the amount of overlap between conditions. NAP is defined as the number of comparison pairs between phases A and B without overlap divided by the total comparisons. It is related to Tau, another overlap metric. Tau is a linear re-scaling of NAP (Zimmerman et al., 2018). NAP offers several advantages over other overlap-based effect sizes, including less human error in calculations (can be calculated by hand or via computerized methods), stronger validation by R^2 , and narrower confidence intervals (Parker & Vannest, 2009). Parker and Vannest (2009) tentatively suggest the following guidelines for NAP effect sizes: .93 – 1.00 = large, .66 – .92 = medium, and 0 – .65 = weak.

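### RQ6 and RQ12 credit retention to the higher maintenance path, which mixes the level reached in teaching with forgetting when a set enters maintenance unmastered

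*Combined protocol and SAP*

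**What the plan says.** **When teaching stops (Section 5.0, Comparison Phase).** Once a child "reaches the criterion of 75% accuracy for expressive labeling for three consecutive sessions for the four target words for one condition", only the other set is taught. If the child "does not reach mastery after two times the number of sessions to criterion in the mastered condition, the maintenance phase begins then". The second set can therefore enter maintenance without having met criterion.

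**Maintenance (Section 5.0, Maintenance Phase).** "Maintenance data are first collected a week after the participant achieves mastery for at least one condition". "Sessions continue for 4 weeks after the comparison phase to permit sufficient time for a trend to emerge for visual analysis", with earlier stopping if the pattern is consistent.

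**What efficiency means (Section 8.0, Efficiency, under both Feedback and Spacing).** The questions are whether one condition reaches mastery faster and "whether mastery-level performance is better maintained".

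**How RQ6 and RQ12 are decided (Section 8.0).** For RQ6, separation of the paths "in the maintenance phase would provide evidence of greater efficiency for the condition with the path that is displayed higher on the graph". RQ12 has the same rule for spacing. One further item is named for both: "The number of sessions to fall below mastery is also considered".

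**Effect size (Section 8.0, Statistical Analysis).** NAP is applied to the same contrasts as the visual analysis, with bands of .93 to 1.00 (large), .66 to .92 (medium) and 0 to .65 (weak).

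The plan does not relate the maintenance path to each set's level when its teaching ended, and it does not say how capped children enter RQ6 and RQ12.

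**The concern.** A capped set has, by definition, not met criterion. Its maintenance path can lie lower because fewer words were learned, even if none of them was lost. RQ5 and RQ11 already credit the other condition for that difference, through the higher comparison-phase path and the sessions to mastery. Under the height rule, RQ6 and RQ12 can credit it again under the name of retention.

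The supporting measure does not correct this. For a set never mastered, the count of sessions until it falls below mastery is undefined; read as zero, it favours the mastered set again.

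Eight participants address each factor and verdicts are combined across them, so a few capped children could shape a conclusion. The cap is also most likely to apply where the two conditions differ most in acquisition.

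**Working it through.** The plan gives no power or sample-size figure on this point, so there is nothing to reproduce. The check asks whether the rule separates two sets that forget at the same rate.

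**Inputs from the documents:** four words per set; criterion of 75% in three consecutive sessions; three comparison sessions per week; cap at two times the sessions to criterion; weekly maintenance over 4 weeks; the NAP bands.

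**Assumptions, not in the documents:** one expressive trial per word (Section 5.0 defines accuracy as correct responses over total trials but does not give trials per word); the starting levels; weekly proportional retention r; the cap read as total sessions.

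**1. Illustration.** The mastered set goes from 4 to 3 words, 100% to 75%, and keeps 3/4 = 75% of what it had. The capped set stays at 2 words, 50% to 50%, and keeps 2/2 = 100%. Path height favours the mastered set by 75 − 50 = 25 points, although only that set lost a word. Likewise, two sets mastered at 3 and 4 words start maintenance 100 − 75 = 25 points apart before any forgetting.

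**2. Same forgetting, same delay, no noise.** Level in week k = start × r^k, for k = 1 to 4. NAP = share of the 4 × 4 = 16 pairs in which the mastered set is higher, ties counting half.
- Starts 75 and 50, r = 0.9: 67.5, 60.8, 54.7, 49.2 against 45.0, 40.5, 36.5, 32.8. All 16 pairs favour the mastered set, so NAP = 16/16 = 1.00.
- Starts 75 and 50, r = 0.8: 60.0, 48.0, 38.4, 30.7 against 40.0, 32.0, 25.6, 20.5. Favourable pairs: 4 + 4 + 3 + 2 = 13, so NAP = 13/16 = 0.81.
- Over starts 100/50, 75/50 and 75/25 and r from 0.7 to 1.0, NAP is 0.81 to 1.00: always medium or large.

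Expressed as a share of its own starting level, each set stands at r^k every week, so the difference disappears.

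**3. With binomial noise, and with a lag.** Each probe is a draw from four words; 5,000 runs per setting. If criterion is met at session 9 and the cap is session 18, the mastered set has gone (18 − 9)/3 = 3 weeks longer without teaching. NAP above 0.50 favours the mastered set.

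| Start probabilities (mastered, capped) | r | Mean NAP, equal delay | Mastered path higher | Mean NAP, 3-week lag | Mastered path higher |
|---|---|---|---|---|---|
| 0.90, 0.50 | 1.0 | 0.898 | 99.3% | 0.896 | 99.4% |
| 0.90, 0.50 | 0.9 | 0.803 | 95.3% | 0.623 | 69.1% |
| 0.90, 0.50 | 0.8 | 0.733 | 89.2% | 0.471 | 36.0% |
| 0.85, 0.50 | 1.0 | 0.856 | 97.8% | 0.856 | 97.9% |
| 0.85, 0.50 | 0.9 | 0.769 | 92.3% | 0.606 | 66.0% |
| 0.85, 0.50 | 0.8 | 0.706 | 85.3% | 0.455 | 33.1% |

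**4. Both sets mastered at 0.90.** With equal delay, mean NAP is about 0.50. With a three-week lag it is 0.302 at r = 0.9 and 0.244 at r = 0.8, against the set mastered first. Height is thus sensitive to delay as well as to starting level.

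**The case against.** **Height is not the only criterion.** Visual analysis covers level, trend, variability, overlap and consistency, and maintenance is run long enough for a trend to show. In the illustration the trends differ, and an analyst should notice. A reader might infer that height alone decides RQ6 and RQ12; the documents do not say that. But height fixes which condition is credited, and NAP also compares raw levels, so the objection softens the point without removing it.

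**Words still known at follow-up is a legitimate outcome.** This stands. In the illustration the mastered set at 75% is still at criterion and the capped set is not, so crediting it can be squared with the stated aim. That the aim presupposes mastery of both sets is an inference. Still, absolute retention is already addressed against control in RQs 3, 4, 9 and 10, and a difference in words known is not by itself a difference in forgetting.

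**Not every capped child is affected in the same direction.** A reader might infer that RQ6 or RQ12 must repeat the RQ5 or RQ11 verdict whenever the cap applies. The documents do not support that: the earlier-mastered set stops being taught first, and with fast forgetting the carry-over shrinks or reverses, as the table shows.

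**Change from own level has a bias too.** A mastered set's last three probes are the ones that met criterion, so they are selected upward. With four independent one-trial words, the expected score given at least 3 of 4 correct is 85.7% when the true probability is 0.75, and 92.3% when it is 0.90. With no forgetting, these would show apparent losses of 85.7 − 75 = 10.7 and 92.3 − 90 = 2.3 points. A capped set has no such selection. This must be stated with the fix.

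**Conclusion.** The point holds as a tendency. As written, RQ6 and RQ12 can count an acquisition difference as better retention in capped children, and to a lesser degree when two sets are mastered at different levels. At equal delay since teaching, identical forgetting gives NAP of 0.81 to 1.00 without noise and a mean of 0.71 to 0.90 with it. With an assumed three-week lag the mean ranges from 0.46 to 0.90, so the effect can vanish or reverse. In either case path height does not isolate retention.

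The gap in the text is certain; its practical size is not. The documents give no expected share of capped children, and the figures rest on assumed starting levels, retention rates, one trial per word and a total-session reading of the cap. A reader might also infer that the cap itself is faulty; nothing here shows that. The correction should be made before RQ6 and RQ12 are analysed, and it belongs in the analysis plan only.

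**What to change.** Amend Section 8.0 for RQ6 and RQ12:

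1. Show each set's end-of-teaching level (for example, its last three probes while still taught) beside its maintenance path.
2. Base the retention verdict on change from that level at comparable time since that set was last taught, not on height alone.
3. Use the count of sessions to fall below mastery only for sets that reached mastery.
4. Report capped children separately, and do not count a higher path in them as evidence of better retention.
5. Keep the raw-height comparison as a description of words known at follow-up.
6. Leave RQs 3, 4, 9 and 10, the teaching procedure and the cap unchanged.

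**Cost.** Revised wording and one extra plot per child, from probes already planned. The plan should also state the downsides:
- Fewer children contribute to the RQ6 and RQ12 verdict.
- Limiting it to children who mastered both sets selects on a post-treatment outcome, so those results should stand alongside the results for all children.
- With four words per set, denominators are small.
- The last-three-probe level of a mastered set is selected upward, so small apparent losses should not be read as forgetting.
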